7.3 Other Exploratory Measures

Exploratory measures include:

1. Measures of MA subjective effects:
 - a. MA withdrawal, as measured by scores on the ACSA during Weeks 1-12
 - b. MA craving as measured by the VAS during Weeks 1-12
2. Measures of opioid subjective effects:
 - a. Clinician rating of opioid withdrawal as measured by the COWS on the day of randomization; each subsequent visit during induction in Week 1, if needed; prior to each injection in Weeks 1, 5, and 9, and at Week 12

- b. Self-reported rating of opioid withdrawal as measured by the SOWS on the day of randomization; each subsequent visit during induction in Week 1, if needed; prior to each injection in Weeks 1, 5, and 9, and at Week 12
 - c. Self-reported opioid craving as measured by VAS, during Weeks 1-12
3. Self-reported craving for MA and opioid co-use as measured by VAS, during Weeks 1-12
4. Measures of mood, pain, and stress:
 - a. Changes in self-reported depressive symptoms as measured by the IDS-SR during Weeks 1-12
 - b. Changes in self-reported anxiety symptoms as measured by the GAD-7 during Weeks 1-12
 - c. Changes in self-reported mood symptoms as measured by the CAST during Weeks 1-12
 - d. Changes in self-reported anhedonia as measured by the DARS during Weeks 1, 5, 9, and 12
 - e. Changes in reported pain as measured by the P-FIBS during Weeks 1-12
 - f. Changes in self-reported stress as measured by the PSS during Weeks 1, 5, 9, and 12
5. Retention:
 - a. Participants retained in treatment, defined as present and providing urine drug samples during Weeks 1-12
6. Measures of Infectious disease control, incidence, and risk:
 - a. Biomarkers measured at Week 12:
 - i. HIV-Negative Participants: Remaining HIV-negative obtained via blood tests
 - ii. HCV-Negative Participants: Remaining HCV-negative obtained via blood tests
 - b. Self-Reported HIV transmission risk behaviors measured at Weeks 1, 6 and 12:
 - iii. Self-reported number of new sexual partners
 - iv. Self-reported number of sexual partners with condomless sex who are serodiscordant or unknown serostatus
 - v. Self-reported number of sexual partners with condomless sex who are serodiscordant or unknown serostatus with whom illicit substances were used during sex (chemsex)
 - vi. For men, self-reported number of male sexual partners
 - vii. Self-reported number of episodes sharing needles
 - viii. Self-reported number of episodes sharing injection equipment and paraphernalia
7. Measures of functioning:
 - a. Changes in self-reported assessment of Quality of Life (QoL) at Week 1 and 12
 - b. Self-reported overall functioning as measured by the Treatment Effectiveness Assessment (TEA) at Week 12

RESTRICTED

8. Measures of adverse events:
 - a. Number and severity of adverse events reported during Weeks 1-12
 - b. Number and outcomes (non-fatal, fatal) of overdose events during Weeks 1-12
9. Self-reported measures of alcohol, tobacco and other drug use on TLFB at Weeks 1, 5, 9, and 12, and UDS results of other substance use not quantified for primary or secondary outcomes.
10. Urinalysis results indicating a new chlamydia or gonorrhea diagnosis at Week 12
11. IGT performance at screening

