6.1.1 Sublingual Buprenorphine Induction

Due to an inability to obtain placebo sublingual medication that is matched to sublingual buprenorphine in appearance and taste, starting on Day 0 of Week 1, participants in both conditions will receive two 4mg doses of sublingual buprenorphine (as SuboxoneTM, Indivior), followed by two 8mg doses on Day 1 and, if necessary, Day 2 to reach 16mg maximum oral dose.

This is designed to facilitate rapid transition to the injectable formulation while ensuring the safety of the participants and helping to support the blinded injectable phase.

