7.2 Secondary Outcome Measures

Secondary outcome measures include:

1. Alternate measures and composites of methamphetamine use:
 - a. MA Treatment Effectiveness Score (TES), as measured by number of UDS results negative for MA by condition, during Weeks 1-12 (possible 2 per week; score range 0-24)
 - b. Self-reported days of MA use on the TLFB during Weeks 1-12 (possible 1 per day; score range 0-84)
2. Measures of opioid use:
 - a. Opioid Treatment Effectiveness Score (TES), as measured by number of UDS results negative for opioids by condition, during Weeks 1-12 (possible 2 per week; score range 0-24). Results from radio-immune assay strips will be used to measure opiates (OPI-300), oxycodone/synthetic opioids, fentanyl for each UDS.
 - b. Self-reported frequency of opioid use on the TLFB during Weeks 1-12. Reports of any opioid used will be combined into one measure that includes opiates, oxycodone and synthetic opioids, fentanyl and analogues for each report during Weeks 1-12 (possible 1 per day; score range 0-84).
3. Measures of MA and opioid co-use:
 - a. MA and Opioid Co-Use compiled using Treatment Effectiveness Score (TES), as measured by number of UDS results negative for both MA and opioids by condition, during Weeks 1-12 (possible 2 per week; score range 0-24)
 - b. Self-reported days of MA and opioid co-use on the TLFB during Weeks 1-12 (possible 1 per day; score range 0-84)

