10.4 Study Intervention(s) Administration

10.4.1 Induction Phase

Participants will receive sublingual film (BUP) on the day of randomization (Day 0) following randomization and collection of assessments required on the day of randomization. If a participant reports symptoms of withdrawal or side effects, ancillary medications may be used to manage symptoms. This includes management of head and body aches (e.g., ibuprofen), insomnia (e.g., diphenhydramine), diarrhea (e.g., loperamide) and stomach upset (e.g., bismuth subsalicylate). The Medical Clinician will guide the induction onto study medication using a defined dosing strategy to ensure that participants in either condition receive the exact same induction and that participants tolerate the medication before proceeding to the first injection. The induction phase will last between 2 and 3 days. If needed, participants may have subsequent study visits during the induction phase.

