number of male sexual partners, (f) Self-reported number of episodes sharing needles, and (g) Self-reported number of episodes sharing injection equipment and paraphernalia will each be analyzed using a repeated measures mixed effects model for count data outcomes. If zero-inflation is observed a zero-inflated poisson, negative binomial, or hurdle model will be used depending on which model best fits the data. However, if an outcome has low counts, we may collapse it into a binary (presence/absence) outcome. If the data are very sparse, we may collapse across weeks and use a logistic regression model.

7. *Measures of functioning:*

- a. Changes in self-reported assessment of Quality of Life (QoL) at Week 1 and Week 12 will be analyzed using repeated-measures mixed-effects model, with terms for time, treatment group, treatment group by time interaction, baseline measure of the outcome, and any covariates. Person effects will be random and all other effects fixed.
- b. Self-reported overall functioning as measured by the Treatment Effectiveness Assessment (TEA) at Week 12 will be analyzed using analysis of covariance.
8. *Measures of adverse events:* both (a) Number and severity of adverse events reported during Weeks 1-12 and (b) Number and outcomes (non-fatal, fatal) of overdose events during Weeks 1-12 will be analyzed using Chi-square tests for each measure of AEs.
9. Self-reported measures of alcohol, tobacco and other drug use on TLFB at Weeks 1, 5, 9, and 12, and UDS results of other substance use not quantified for primary or secondary outcomes will be analyzed using a repeated-measures mixed-effects model for continuous outcome (amount of use) or binary outcome (presence/absence of use). The models will have terms for time, treatment group, treatment group by time interaction, baseline measure of the outcome, and any covariates. Person effects will be random and all other effects fixed.
10. Urinalysis results indicating a new chlamydia or gonorrhea diagnosis at Week 12 will be analyzed using a logistic regression with the presence of a Week 12 diagnosis as the outcome and treatment group and other covariates and predictors.
11. IGT at screening as a predictor of treatment response will be analyzed using the primary outcome analysis being repeated with the addition of terms for baseline IGT performance and IGT by time interaction.

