16.9 Safety Analysis

Treatment emergent adverse events (AEs), including treatment emergent serious adverse events (SAEs), will be summarized by presenting the number of events, number of participants experiencing AEs, and the severity and relatedness of adverse events by treatment arm. All adverse events will be coded using MedDRA® (The Medical Dictionary for Regulatory Activities). The number and proportion of participants experiencing each treatment emergent AE will be provided overall and by treatment arm. Treatment emergent adverse events will be summarized by System Organ Class (SOC) and Preferred Term (PT). If a participant experiences multiple episodes of an event, then the event is only counted once. Detailed listings of treatment emergent adverse events and non-treatment emergent events in the safety population by treatment arm will be provided and include severity, relationship to study medication(s), and action taken, as available. The criteria for an immediate study review by the DSMB will be monitored closely. These criteria are either (1) three or more participants experience severe adverse reactions; (2) four or more participants have four consecutive positive urine toxicology screens for opioid use,

and have been reevaluated through any means as having moderate to severe opioid use disorder; or (3) one or more SUSAR.

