17.17.3 Adverse Events (AEs)

Standard definitions for adverse events and serious adverse events, their identification, characterization regarding severity and relationship to therapy, and processing are described in Appendix A.

For the purpose of this study, all AEs will require reporting in the electronic data system.

Events that are temporally associated with SL-BUP use, but that are not recorded using either the Medication Side Effects form, or a different study-specific CRF (e.g., withdrawal on the COWS/SOWS, Buprenorphine-XR/Placebo Injection Site Evaluation), will be recorded as an AE.

Events related to the injection of the study medication are recorded on the Injection Site Examination form and will not be duplicate reported on an AE form, unless they meet the SAE definition.

Events related to withdrawal symptoms are captured on the COWS and SOWS forms and will not be duplicate reported on an AE form, unless the event meets the definition of an SAE. Withdrawal symptoms not captured by scheduled COWS and SOWS form should be reported as an AE. Any spontaneous reporting of withdrawal symptoms by the participant will be captured using the AE form in the following situations: withdrawal symptoms reported at visits without scheduled specific structured questionnaires (COWS and SOWS CRFs) and withdrawal symptoms not listed in the specific structured questionnaires (COWS and SOWS CRFs) reported at any visit.

Any of these events that meet the definition of an SAE are reported on the AE/SAE form set.

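### Adverse events are compared by arm from Day 0, so residual events from the 2-3 day active sublingual lead-in modestly dilute the injection comparison; define the treatment-emergent start and tabulate the two periods separately

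*Combined protocol and SAP*

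**What the plan says.** **The window and the test.** Section 7.3 item 8 lists the "Number and severity of adverse events reported during Weeks 1-12" and, over the same weeks, the number and outcomes of overdoses. Section 16.6 item 8 says that these "will be analyzed using Chi-square tests for each measure of AEs". Section 16.9 adds that "The number and proportion of participants experiencing each treatment emergent AE will be provided overall and by treatment arm", and that repeated episodes of one event in a participant count once. It lists non-treatment-emergent events as well, but gives no start point for treatment emergence.

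**The lead-in.** Section 6.1.1 states that "participants in both conditions will receive two 4mg doses of sublingual buprenorphine" from Day 0 of Week 1. Section 10.4.1 puts this after randomization ("Participants will receive sublingual film (BUP) on the day of randomization (Day 0) following randomization") and says "The induction phase will last between 2 and 3 days". The first injection, where the arms diverge, is expected at about Day 3 (Section 6.1.2).

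**Which lead-in events reach the AE form.** Section 11.3.3 puts expected sublingual reactions on a Medication Side Effects form, completed at the second Week 1 visit, and keeps them off the AE form unless serious. Section 17.17.3 does the same for withdrawal symptoms captured on scheduled COWS and SOWS forms. The AE form does receive "Events that are temporally associated with SL-BUP use, but that are not recorded using either the Medication Side Effects form" or another study-specific form, together with withdrawal symptoms that are off-schedule or unlisted on those scales, and all SAEs.

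Neither Section 16.6 nor Section 16.9 separates the lead-in from the injection period. Neither describes an analysis of the Medication Side Effects form.

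**The concern.** The safety question specific to this trial is what the injection adds, and the arms differ only from the first injection onward. A by-arm table that starts at Day 0 includes 2-3 days in which placebo-assigned participants take active buprenorphine. Any AE-form event from those days in a placebo-assigned participant is counted under placebo.

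Adding the same events to both arms pulls participant-level ratios toward 1. The count-once rule in Section 16.9 adds to this: a participant who has an event in the lead-in and the same event again after an injection contributes one occurrence, so the earlier episode can hide the later one. With the treatment-emergent start undefined, two analysts could build the Section 16.9 table differently. Lead-in tolerability is partly mixed into the arm comparison and partly left on a form with no planned summary.

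**Working it through.** The documents state no AE rate, no lead-in event rate and no power for the AE comparison, so there is no plan figure to reproduce. The risks below are assumptions.

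**Inputs from the documents**
- Lead-in length: 2 to 3 days (Section 10.4.1).
- Weeks 1-12: 84 days, from the range of the daily self-report count in Section 7.2.
- 123 per arm: 246 randomized 1:1 (Sections 16.1.3 and 16.2).
- Two-sided 5% level: stated in Section 16.4 for the primary outcome, assumed here for the AE tests.

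**Step 1: share of the window.** 2/84 = 2.4% and 3/84 = 3.6%.

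**Step 2: event rates.** Suppose lead-in events occur at the BUP-Inj rate and nothing is diverted to other forms. With true rate ratio R and a lead-in of d days, the whole-window ratio is 84R / [(84 - d) + dR].
- R = 2: 168/84 → 168/(82 + 4) = 1.95 for d = 2; 168/(81 + 6) = 1.93 for d = 3.
- R = 3: 252/(82 + 6) = 2.86 for d = 2; 252/(81 + 9) = 2.80 for d = 3.

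**Step 3: proportion with at least one event.** Let p be an arm's post-injection risk and q the lead-in risk common to both arms, taken as independent. Whole-window risk is 1 - (1 - p)(1 - q), so the risk difference shrinks by the factor (1 - q). Power uses the two-proportion normal approximation with unpooled variance and 123 per arm. Assume p = 30% on placebo and 50% on BUP-Inj.

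| q | Placebo | BUP-Inj | Difference | Ratio | Power |
|---|---|---|---|---|---|
| 0 | 30.0% | 50.0% | 20.0 points | 1.67 | 90.5% |
| 2% | 31.4% | 51.0% | 19.6 points | 1.62 | 89.0% |
| 5% | 33.5% | 52.5% | 19.0 points | 1.57 | 86.6% |

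**Step 4: is 2-5% a reasonable range for q?** A 50% risk spread evenly over the remaining 81 days implies a 3-day risk of 1 - 0.5^(3/81) = 2.5% before any diversion. Events may cluster at first exposure, which pushes q up. Sections 11.3.3 and 17.17.3 move the non-serious expected reactions and scheduled withdrawal findings elsewhere, which pushes it down.

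**Step 5: a rare single term.** Assume post-injection risks of 3% and 9%, a ratio of 3.0.
- q = 2%: 1 - 0.97 × 0.98 = 4.9% and 1 - 0.91 × 0.98 = 10.8%; ratio 2.2.
- q = 5%: 1 - 0.97 × 0.95 = 7.9% and 1 - 0.91 × 0.95 = 13.6%; ratio 1.7.

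**Step 6: mean event counts.** The lead-in follows randomization and is the same in both arms. It adds the same expected number of events to each arm and cancels from the difference in means.

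**The case against.** The strongest objection is that this is not a bias. Counting from randomization compares the two regimens as assigned, and an identical lead-in cannot create a difference between arms. The lead-in is at most 3.6% of the window, and its commonest reactions are recorded on other forms. The measure is exploratory, the plan tests it by chi-square rather than estimating ratios, and it claims no power for it. Section 16 describes itself as a general account with a formal SAP to follow. All of this stands and limits the point to interpretability.

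For Section 16.9, the undefined start also means that nobody can say for certain that lead-in events enter that table. That is correct, and the missing definition is itself part of the point. It does not affect Sections 7.3 and 16.6, where the window is stated.

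Separating the periods also has limits. Section 4.2.4 expects mild withdrawal in placebo participants from the 2-3 days of sublingual drug. Its onset can follow the first placebo injection, so a post-injection table would still count it under placebo. That table also conditions on having been injected.

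A reader might go further and infer that reactions to active drug are generally booked to placebo, with lead-in risks of 10-30% and a large loss of power. The documents do not support this: the diversion rules leave only a residue, and nothing in the text gives AE-form risks of that size over 2-3 days. A reader might also infer that a single lead-in SAE or overdose under placebo shows a systematic distortion. Such an event is equally likely in either arm, so it is chance.

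**Conclusion.** The point holds in a limited form. The Weeks 1-12 by-arm measures include a short period of active drug in both arms, no analysis separates it, and treatment emergence has no defined start. The comparison remains valid as a comparison of assigned regimens; what is diluted is the participant-level proportion or ratio as a description of the injection.

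The dilution is modest for any-AE summaries: about 0.04 to 0.10 on a ratio of 1.67, and roughly 1.5 to 4 percentage points of power. It is larger for uncommon individual terms. These sizes rest on assumed post-injection risks, an assumed lead-in risk of 2-5%, independence between periods and a 5% two-sided test. The structural finding needs none of those assumptions. It is a low-cost improvement to an exploratory safety analysis and leaves the primary efficacy analysis untouched.

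**What to change.** In Section 16.6 item 8 and Section 16.9, and in the SAP:

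1. State the date from which an event is treatment-emergent.
2. Tabulate AEs, SAEs and overdoses in two periods. The first runs from Day 0 to just before the first injection, pooled as sublingual buprenorphine and also shown by arm, with the Medication Side Effects form summarized alongside. The second runs from the first injection onward, by arm, among participants who were injected.
3. Apply the count-once rule within each period.
4. Keep the all-randomized Weeks 1-12 by-arm table, because the post-injection table is restricted to those who received an injection.
5. Add a note that withdrawal from the lead-in can appear after the first placebo injection, so the second period does not fully isolate the injection.

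The cost is SAP wording and one more set of tables, built from event-onset and injection dates that the trial already records. No data collection or trial procedure changes.

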7.4 Study Timeline

After receiving Center for the Clinical Trials Network (CCTN) approval of the full and final protocol, approximately 8 months of trial preparation activities will elapse prior to commencing enrollment. Trial preparation will include applying for and obtaining Institutional Review Board (IRB) approval, filing the IND application, developing the data collection systems, developing the Manual of Procedures (MOP), conducting all staff training, collecting required regulatory documents, and endorsing sites. If feasible, the study may be implemented in a single wave; however, sites may launch on a rolling basis. Recruitment is expected to take approximately 18 months, with the medication phase and follow-up continuing for approximately four months post completion of the recruitment phase. Two months will be allowed for data lock after the end of the follow-up period. Therefore, data lock is projected to occur at approximately 32 months after CCTN approval of the final protocol.

8.0 STUDY POPULATION

Approximately 246 males and females who meet eligibility criteria will be randomized. Eligible participants will meet criteria for moderate to severe MUD and have co-occurring mild OUD or opioid misuse not warranting MOUD.

8.1 Participant Inclusion Criteria

Individuals must meet all of the inclusion criteria in order to be eligible to be randomized into the study.

Study participants **must**:

1. Be 18 to 65 years of age, inclusive;
2. Able to understand and speak English or Spanish;
3. Be interested in reducing or stopping MA use and not interested in pursuing MOUD;
4. Meet DSM-5 criteria for moderate or severe MUD (4 or more criteria);
5. Self-report MA use on 18 or more days in the 30-day period prior to written consent using the TLFB;
6. Provide at least 2 urine samples positive for MA out of a possible 3 tests to occur at clinic visits within a 10-day period with at least 2 days between visits;
7. Meet DSM-5 criteria for mild OUD (at least 2 but no more than 3 criteria) prior to randomization OR opioid misuse demonstrated by self-report of opioid use of at least 2 days in the 30-day period prior to written consent using the TLFB;
8. Provide at least 2 urine samples negative for opioids, at least one during the screening period and again on the day of expected randomization to indicate control over opioid use;
9. Have a COWS score of ≤8 at both the screening visit on which they provide a UDS negative for opioids and on the day of randomization;
10. If female, agree to both of the following: use an acceptable method(s) of birth control, as defined in the MOP, for the duration of study participation and for four months after the last injection of study medication; undergo periodic urine pregnancy tests for the duration of study participation, unless verifiably unable to get pregnant, as defined in the MOP;
11. Be willing and able to provide consent and comply with all study procedures and medication instructions;

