4.2.4 Ethical considerations of placebo for mild OUD or opioid misuse

The issue of implementing an ethical placebo control condition in this trial of BUP-Inj for persons with moderate-to-severe MUD who co-use opioids (mild OUD or opioid misuse) requires careful consideration. First, participants to be included in this trial will have moderate-to-severe MUD as the primary substance use disorder being treated. We have included procedures to ensure that participants who have moderate-to-severe OUD co-occurring with moderate-to-severe MUD will instead be assisted in seeking medication for OUD and not enrolled in this research project. To support the diagnosis of mild OUD or opioid misuse, participants are required to produce at least one urine sample negative for opioids during the screening phase and a second urine sample negative for opioids on the day of randomization, and self-report at least two days of opioid use in the 30-day period prior to written consent using the TLFB. Potential participants who under-represent the severity of their OUD during screening and present with opioid withdrawal symptoms will be excluded and referred to medication for OUD. Severity of withdrawal symptoms will be evaluated by the COWS. An inclusion criterion requires all participants report a score of ≤ 8 at both a screening assessment when the participant tests negative for opioids and on the day of randomization. The protocol has an inclusion criterion requiring participants to meet moderate-to-severe MUD and co-use opioids at a level that meets criteria for mild OUD or opioid misuse demonstrated by self-report of any use on the TLFB. Note that in the context of potential participants having moderate-to-severe MUD, any opioid use is considered misuse. Included participants may report physical symptoms of opioid tolerance and withdrawal, though cannot have criteria signaling severe opioid addiction. These procedures ensure selection of participants with moderate-to-severe MUD and mild opioid use disorder or opioid misuse as these participants do not warrant treatment with medication for OUD under standard clinical care. Potential participants whose opioid use does not allow for 48-72 hours without using opioids are excluded and instead referred to medication for opioid use disorder in their communities.

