There will be approximately 246 individuals randomized into the study across 4-8 clinical sites. Eligibility will be determined during a maximum 21-day screening period. To document an appropriate level of current MA use, prospective participants must have at least two positive UDS for MA out of a possible three tests to occur at clinic visits within a 10-day period, with at least two days between visits. In addition, participants must self-report MA use on 18 or more days in the 30-day period prior to written consent using the TLFB and meet diagnostic criteria for moderate or severe MUD per DSM-5 (four or more criteria) at screening. In addition, prospective participants must also meet diagnostic criteria for mild opioid use disorder per DSM-5 (at least two but no more than three criteria) at screening or demonstrate opioid misuse by self-reporting opioid use on at least two days in the 30-day period prior to written consent using the TLFB. Additionally, participants must also provide a UDS negative for opioids at least once during the screening period and on the day of randomization, to demonstrate the ability to abstain from using opioids for a short period of time and have a COWS score of ≤ 8 at both a screening visit on which they provide a UDS negative for opioids and on the day of randomization. After screening is completed and eligibility is confirmed, participants will begin the 12-week medication phase of the trial. Participants will be randomized to receive either 1) BUP-Inj or 2) PBO-Inj. Injections will be provided in Weeks 1, 5, and 9. Participants will be asked to submit twice weekly urine samples, and complete once-weekly cognitive behavioral therapy based on a treatment manual adapted for stimulant use disorder specifically for this study. Participants will be asked to complete assessments as indicated on the schedule of assessments (see Section 11).

The experimental treatment and placebo will be in injectable formulation, with the addition of a two- to three-day sublingual buprenorphine induction using a defined dosing strategy for titration prior to initiating the injections. Dosing will be as follows:

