10.2.3 Screening Assessments

After signing the IRB-approved consent form, participants enter into a maximum 21-day screening phase to complete assessments to determine eligibility. Screening assessment procedures must be completed across at least two screening visits.

During the screening phase, participants must have at least 2 positive UDS for MA out of a possible 3 tests that must occur within a 10-day period, and at least 2 full days must pass between clinic visits. In addition, participants must self-report MA use on 18 or more days in the 30-day period prior to written consent using the TLFB. These criteria will be used to confirm current MA use and further substantiate a diagnosis of moderate to severe MUD.

In addition, the participant must meet DSM-5 criteria for mild OUD (at least 2 but no more than 3 criteria) or self-report opioid use on at least 2 days in the 30-day period prior to written consent using the TLFB. Additionally, at least once during the screening period and again on the day of expected randomization, the participant must provide a urine sample that is negative for opioids to demonstrate the ability to abstain from using opioids for a short period of time. The urine can be positive for MA. On these visits that the participant provides the required opioid-negative urine samples, the participants must also report a COWS score ≤ 8 to indicate opioid withdrawal symptoms do not present at moderate or severe levels (supporting that the participant has mild opioid use disorder or opioid misuse). If on the day of randomization, the participant instead provides a urine sample that is positive for opioids, they cannot be randomized to the study on that day and must delay study participation for at least one month. After at least one month, they can restart the screening phase. This is allowed only one time per participant in the course of the study.

A physician (MD or DO) who serves in the Site PI or Medical Clinician study role must review and approve safety and eligibility assessments in order to confirm participant eligibility prior to randomization after the participant does the following:

1. Completes all screening assessments,
2. Has 2 MA-positive UDS tests and 1 opioid-negative UDS test per guidelines above,
3. On the day randomization is expected, has a urine sample negative for BUP, methadone, and opioids (but can be positive for MA) and if capable of getting pregnant, has a negative urine pregnancy test, and

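### Inclusion criterion 7 caps opioid use disorder severity on one of its two branches only, so the numbered criteria do not enforce the severity limit stated in section 4.2.4

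*Combined protocol and SAP*

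**What the plan says.** Criterion 7 of section 8.1 offers two ways in, joined by OR. The first is mild OUD, at least 2 and "no more than 3 criteria) prior to randomization OR opioid misuse demonstrated by self-report of opioid use of at least 2 days"; the words after OR are the second. The design overview in section 6.1 has the same form, "no more than three criteria) at screening or demonstrate opioid misuse by self-reporting opioid use on at least two days". So does section 10.2.3, where the alternative to mild OUD is "or self-report opioid use on at least 2 days in the 30-day period prior to written consent using the TLFB". Section 24.1 repeats it.

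The descriptions of the population are narrower. Section 8.0 says that eligible participants "have co-occurring mild OUD or opioid misuse not warranting MOUD". Section 4.2.4 says that "participants who have moderate-to-severe OUD co-occurring with moderate-to-severe MUD will instead be assisted in seeking medication for OUD and not enrolled".

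Section 4.2.4 is not consistent with itself:

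- **Ceiling.** Besides the bar on moderate-to-severe OUD, it says that participants may report tolerance and withdrawal symptoms, "though cannot have criteria signaling severe opioid addiction".
- **Floor.** It says participants must "self-report at least two days of opioid use in the 30-day period prior to written consent using the TLFB", but later describes the criterion as "mild OUD or opioid misuse demonstrated by self-report of any use on the TLFB". It adds that any opioid use in this population counts as misuse.

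**The concern.** Section 4.2.4 defends the placebo arm on the ground that the people selected do not need medication for OUD (MOUD) under standard care. That defence holds only if the entry rules keep out people with more severe OUD. Sites work from the numbered list in section 8, and the Enrollment form (section 11.7.2) reproduces that list. If the list lets in a person with 4 or more OUD criteria, that person can be randomized to placebo with no deviation from the eligibility criteria.

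Entry would then also be looser than the review during the trial. Under section 10.7, a participant whose repeated opioid positives trigger a review continues if opioid use is judged to be no worse than mild OUD. The DSMB trigger in section 10.8 counts participants with four consecutive positives who are re-evaluated as having moderate to severe OUD. Someone at that level on entry would meet the severity half of the trigger from the start, which weakens it as a sign of worsening.

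**Working it through.** There is no stated figure to reproduce; this is a check of logic.

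**Inputs.** Let c be the number of DSM-5 OUD criteria met and d the self-reported opioid-use days in the 30 days before consent (0 to 30). Section 8.1 defines mild OUD as 2 to 3 criteria. For methamphetamine use disorder it counts 4 or more criteria as moderate or severe, so on that scale c of 4 or more lies above mild.

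**Criterion 7 as written.** Pass if (2 ≤ c ≤ 3) OR (d ≥ 2).

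**Criterion 7 with its ceiling on both branches**, for comparison only. Pass if c ≤ 3 AND [(2 ≤ c ≤ 3) OR (d ≥ 2)].

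| OUD criteria c | Use days d | As written | Ceiling on both branches |
|---|---|---|---|
| 1 | 0 or 1 | fail | fail |
| 1 | 2 or more | pass | pass |
| 3 | any | pass | pass |
| 4 or more | 0 or 1 | fail | fail |
| 4 or more | 2 or more | **pass** | **fail** |

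As written, the ceiling can exclude someone only at d = 0 or 1. For d = 2 to 30 it does nothing: 30 − 2 + 1 = 29 of 31 values.

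**Full grid.** Take c from 0 to 11 (the upper end is an assumption and does not affect the conclusion) and d from 0 to 30, so 12 × 31 = 372 combinations.

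- As written: 2 × 31 = 62 pass at c = 2 or 3, and 10 × 29 = 290 at the other counts; total 352.
- Ceiling on both branches: 62 pass at c = 2 or 3, and 2 × 29 = 58 at c = 0 or 1; total 120.
- Difference: 352 − 120 = 232 = 8 × 29, all with c ≥ 4 and d ≥ 2. Eligibility at c = 0 to 3 does not change.

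These are logical combinations, not proportions of people.

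**Does another numbered criterion supply the limit?** There are 11 inclusions and 15 exclusions, 26 in all.

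- Inclusion 8 (two opioid-negative urines) limits recent use.
- Inclusion 9 (COWS of 8 or less at two time points) limits current withdrawal.
- Inclusion 3 and exclusion 7 concern interest in MOUD and current treatment.
- Exclusion 6 bars prescribed or taken buprenorphine or methadone within 30 days.
- Exclusion 15 is clinician discretion, with no OUD rule.

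None names OUD severity or a maximum criteria count for the misuse branch. The requirement in section 4.2.4 to manage 48 to 72 hours without opioids is not in the numbered list. The words in section 8.0 about not warranting MOUD have no stated measurement.

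**The use-day minimum.** If the two-day minimum in section 4.2.4 applies to everyone, all participants satisfy the OR branch and the ceiling never excludes anyone. If it applies only to the misuse branch, section 4.2.4 is worded more broadly than section 8.1.

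**The case against.** The best defence is that the limit works indirectly. Section 4.2.4 lists the opioid-negative urines, the COWS limit and the other conditions, and concludes that together they select people with mild OUD or misuse. Section 10.2.3 treats the COWS limit as support for that status. A physician must approve eligibility before randomization, and section 24.2 also asks for an evaluation that the person is eligible and safe to enter. The documents often pair mild OUD with misuse not warranting MOUD, so misuse can be read as a category at or below mild OUD. The remark about severe addiction may only describe which symptoms are acceptable, and the phrase about any use is a single summary sentence in a background section.

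Part of this stands. These conditions make entry by someone with more severe OUD less likely, the intent is fairly clear, and the any-use wording is minor because all four operative statements say two days. But the conditions measure recent use, withdrawal and preference, and the discretionary ones may be applied differently across the 4 to 8 sites. No text confines misuse to people below a criteria count: criterion 7 defines it by use days, and section 4.2.4 widens it to any opioid use. The physician reviews eligibility against criteria that contain no such limit. Naloxone kits, the offer of MOUD and the review after four consecutive positives act only after randomization.

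**Conclusion.** The concern holds and should be corrected. The four places that set out the criterion (sections 6.1, 8.1, 10.2.3 and 24.1) share the same gap. None of the 26 numbered criteria fills it, and the result contradicts the statement in section 4.2.4 about who is not enrolled. The conclusion rests on reading criterion 7 as printed and on the absence of any written definition that restricts misuse to lower criteria counts.

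How many participants could be affected is unknown, because the documents give no distribution of OUD criteria in the screened population. The power simulation in section 16.2 does not use OUD severity, so the sample size of 246 and the primary analysis stand. What is at stake is participant protection and the stated justification for placebo.

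**What to change.** Reconcile sections 6.1, 8.1 (criterion 7), 10.2.3 and 24.1 with sections 4.2.4, 8.0 and 10.7:

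1. Decide which of the two ceilings worded in section 4.2.4 is intended. That is the sponsor's clinical decision, and no threshold is proposed here.
2. State it as one explicit numbered criterion covering both branches, since section 4.2.4 makes no exception for people entering through misuse. Carry it onto the Enrollment form and assess it from the MINI already done at screening (section 11.2.4).
3. Use one wording for the minimum number of opioid-use days, and say whether it applies to everyone or only to the misuse branch.

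The cost is wording in the protocol and the Enrollment form, with no new data collection. Some people who now pass screening would be referred instead of randomized, which could slow recruitment. The sample size and analysis stay as planned.
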